### **Serious Adverse Event**

A serious adverse event is defined as any adverse medical experience that results in any of the following outcomes:

- death;
- is life-threatening;
- requires inpatient hospitalization or prolongation of existing hospitalization;
- results in persistent or significant disability/incapacity;
- is a congenital anomaly/birth defect; or
- requires medical or surgical intervention to prevent permanent impairment or damage.

**Opioid-related adverse** (i.e. respiratory depression, pruritus, sedation, delirium) within the first 48 hours after the end of surgery.

[figure not shown]
**Postoperative complications** will be recorded using Clavien-Dindo scale and POMS.

### **Statistical Considerations**

The primary objective of evaluating the impact of 4 quadrants TAP blocks (4Q-TAP) versus Thoracic Epidural Analgesia (TEA - routine care) on the quality of recovery (QoR) will be conducted using total scores on each patient acquired from the QoR-15. The QoR-15, as previously mentioned, is a validated instrument with well-studied psychometric properties used to measure postoperative quality of recovery. The QoR-15 consists of 15 items. All 15 items follow a Likert scale ranging from 0 to 10 (where “0” refers to none of the time [poor] and “10” refers to all of the time [excellent]). A patient’s total score is the sum score across all 15

items (note: the last 5 items are reverse scored). The lowest score a patient can receive is “0” and the highest score is “150”; where higher total scores indicate better quality of recovery. To evaluate the trial changes in QoR-15 total scores will be computed for each treatment arm. The changes will be compared between patients receiving 4Q-TAP Block and patients receiving TEA. Figure 1 illustrates the trial’s development over time. Once a patient is randomized and the preoperative QoR-15 is administered, which takes approximately 2.4 minutes to complete, patients will be provided postoperative QoR-15 approximately 26 hours after surgery (Figure 1: [A]; Stark et al). Within patient changes from baseline will be computed for each treatment arm. These changes will be compared between treatment arms (Figure 1: [B]).

Figure 1: Trial Schema

This randomized trial will be used to determine if 4Q-TAP Block is non-inferior to TEA based on postoperative changes in QoR-15 using a non-inferiority margin of 10 units. According to Stark et al., the reported mean change in QoR-15 before and after surgery is -22 (95%CI: -26 to -18) based on 127 adults. This information allowed us to assume of a common standard deviation of 23 units for the change in QoR-15’s total score pertaining to each treatment arm, which was ultimately used to derive the study’s sample size.

[figure not shown]
The following hypothesis test will be used to evaluate the trial:

$$H_0: \mu_{4Q-TAP\ Block} - \mu_{TEA} \geq 10.0$$

$$H_a: \mu_{4Q-TAP\ Block} - \mu_{TEA} = 0 \text{ (rejecting } H_0 \text{ implies non-inferiority)}$$

We will use a one-sided t-test test with a significance level of 0.05 and power of 80%. A non-inferiority margin of 10 was considered by assuming an average change in QoR-15 of -25 units in the TEA arm and that the average change in QoR-15 for the 4Q-TAP Block treatment arm would be no greater than -35.

Figure 2: Non-inferiority assessment

These specifications require an approximate sample size of 140 patients as indicated in Table 1. Moreover, an interim analysis will be conducted at after 70 patients are randomized using stopping boundaries provided by the method of Pock and Simon. At the interim, the trial will stop early if  $p < 0.006$  for efficacy and  $p > 0.367$  for futility (East v6).

Table 1: Estimated sample size given projected study parameters

Expected QoR-15 Avg. Change * for Epidural group	Non-inferiority Margin	Power	Alpha (1-sided)	Approx Sample Size
-25	10	80%	5%	140

\*Avg. Change before and after surgery; Assumed SD = 23; A non-inferiority margin of 10 implies the Avg. Change for TAP will be -35 [ie.  $-25 - (-35) = 10$ ]

\*Sample size for the difference of two means using a two sample test (East v6).

The data will be evaluated per protocol for patients contributing analyzable data.

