## 1. STUDY SYNOPSIS

Four quadrant TAP (4Q-TAP) block with plain and liposomal bupivacaine vs. Thoracic Epidural Analgesia (TEA) in patient's undergoing cytoreductive surgery with hyperthermic intraperitoneal chemotherapy (CRS-HIPEC) on an enhanced recovery pathway: a single-blinded, randomized, non-inferiority study.
	

Objectives
	
To evaluate the impact of 4 quadrants TAP blocks (4Q-TAP) versus Thoracic Epidural Analgesia (routine care) on the quality of recovery and other clinically relevant outcomes after CRS-HIPEC surgery.
 
To study the incidence of adverse events associated with (4Q-TAP) blocks versus Thoracic Epidural Analgesia (routine care) after CRS-HIPEC surgery.

Aims
	
a. Primary Aim: To compare the efficacy of 4 quadrants TAP blocks (4Q-TAP) versus Thoracic Epidural Analgesia (routine care) on the quality of recovery 48 hours after CRS-HIPEC surgery.
 
b. Secondary Aim 1: To compare the efficacy of 4 quadrants TAP blocks (4Q-TAP) versus Thoracic Epidural Analgesia (routine of care) on postoperative pain 48 hours after CRS-HIPEC surgery.
 
c. Secondary Aim 2: To compare the total opioid consumption between patients with 4 quadrants TAP blocks (4Q-TAP) versus Thoracic Epidural Analgesia (routine care) intraoperatively and up to 48 hours after CRS-HIPEC surgery.
 
d. Secondary Aim 3: To compare the length of stay (LOS) between patients with 4 quadrants TAP blocks (4Q-TAP) versus Thoracic Epidural Analgesia (routine care) after CRS-HIPEC surgery.
 
e. Secondary Aim 4. To compare the incidence of adverse events (i.e. postoperative hypotension, failed block) related to 4 quadrants TAP blocks (4Q-TAP) versus Thoracic Epidural Analgesia (routine care) 48 hours after CRS-HIPEC surgery.
 
f. Secondary Aim 5. To compare the incidence of opioid-related adverse (i.e. respiratory depression, pruritus, sedation, delirium) events related to 4 quadrants TAP blocks (4Q-TAP) versus Thoracic Epidural Analgesia (routine care) 48 hours after CRS-HIPEC surgery.
 
g. Secondary Aim 6. To compare the incidence postoperative complications and morbidity in patients receiving 4 quadrants TAP blocks (4Q-TAP) versus Thoracic Epidural Analgesia (routine care) 48 hours after CRS-HIPEC surgery.

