
Study Design
	
This is a randomized controlled trial designed to test efficacy of 4Q-TAP against TEA (routine of care) on quality of recovery 48 hours after CRS-HIPEC surgery. All patients will be enrolled at MD Anderson Cancer Center.

Number of Patients
	
160 patients randomized to the 2 study arms (80 patients per arm)

Sites
	
MD Anderson Cancer Center

Duration of Study	It is expected that this will take up to 36 months.
Duration of Patient Participation	Patients who consented to participate in the study will remain in the study until last planned outcome is collected on postoperative day 30. Patient will have the opportunity to withdraw from the study at any time.
Primary Endpoint Definition	Quality of recovery (QoR) 48 hours after CRS-HIPEC surgery.
Secondary Endpoints	
 
• Postoperative pain 48 hours
 
• The total opioid consumption within 48 hours after surgery
 
• Length of stay
 
• Incidence of adverse events
 
• Incidence of opioid-related adverse events
 
• Postoperative complications and morbidity
 
• QoR on postoperative day 3, 7 10 and 30.
 

Primary Safety Endpoint	All reported adverse events.
Follow-Up Schedule	The study will be considered complete after all randomized patients have had 30 days of follow-up data collection.
Inclusion Criteria	
 
1. Written informed consent;
 
2. 18 years old or older;
 
3. American Society of Anesthesiologists physical status (ASA) 1-3;
 
4. Scheduled surgery: open elective CRS-HIPEC;
 
5. Able to complete the QoR 15 questionnaire;
 
6. Patients scheduled to receive intraoperative chemotherapy;
 

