## 3. STUDY AIMS

a. **Primary Aim:** To compare the efficacy of 4 quadrants TAP blocks (4Q-TAP) versus Thoracic Epidural Analgesia (routine care) on the quality of recovery 48 hours after CRS-HIPEC surgery.

**Hypothesis:** The quality of recovery with 4 quadrants TAP blocks (4Q-TAP) 48 hs after CRS-HIPEC surgery is not inferior to Thoracic Epidural Analgesia (routine care).

b. **Secondary Aim 1:** To compare the efficacy of 4 quadrants TAP blocks (4Q-TAP) versus Thoracic Epidural Analgesia (routine of care) on

postoperative pain 48 hours after CRS-HIPEC surgery.

**Hypothesis:** Postoperative pain 48 hours after CRS-HIPEC surgery is not inferior with 4 quadrants TAP blocks (4Q-TAP) than Thoracic Epidural Analgesia (routine care).

c. **Secondary Aim 2:** To compare the total opioid consumption between patients with 4 quadrants TAP blocks (4Q-TAP) versus Thoracic Epidural Analgesia (routine care) intraoperatively and up to 48 hours after CRS-HIPEC surgery.

**Hypothesis:** Perioperative opioid consumption after CRS-HIPEC surgery is not higher in patients with 4 quadrants TAP blocks (4Q-TAP) than epidural analgesia (routine care).

d. **Secondary Aim 3:** To compare the length of stay (LOS) between patients with 4 quadrants TAP blocks (4Q-TAP) versus Thoracic Epidural Analgesia (routine care) after CRS-HIPEC surgery.

**Hypothesis:** The LOS after CRS-HIPEC surgery is shorter in patients with 4 quadrants TAP blocks (4Q-TAP) than Thoracic Epidural Analgesia (routine care).

e. **Secondary Aim 4.** To compare the incidence of adverse events (i.e. postoperative hypotension, failed block) related to 4 quadrants TAP blocks (4Q-TAP) versus Thoracic Epidural Analgesia (routine care) 48 hours after CRS-HIPEC surgery.

**Hypothesis:** The incidence of adverse events (i.e. postoperative hypotension, failed block) related to 4 quadrants TAP blocks (4Q-TAP) is lower than Thoracic Epidural Analgesia (routine care) 48 hours after CRS-HIPEC surgery.

f. **Secondary Aim 5.** To compare the incidence of opioid-related adverse (i.e. respiratory depression, pruritus, sedation, delirium) events related to 4 quadrants TAP blocks (4Q-TAP) versus Thoracic Epidural Analgesia (routine care) 48 hours after CRS-HIPEC surgery.

**Hypothesis:** The incidence of opioid-related adverse events is lower in patients receiving 4 quadrants TAP blocks (4Q-TAP) versus Thoracic Epidural Analgesia (routine care) 48 hours after CRS-HIPEC surgery.

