### **D. Liposomal bupivacaine: A long-acting local anesthetic**

The longer duration of analgesia (48-72 hours) with the use of liposomal bupivacaine presents advantages over traditional local anesthetics. A number of

studies support the benefits of liposomal bupivacaine for TAP blocks over standard bupivacaine alone. In a randomized prospective trial by Hutchins et al, patients undergoing robotic hysterectomy and received subcostal TAP with liposomal bupivacaine had lower opioid requirements for the first 72 hours after surgery and lower pain scores when compared to bupivacaine hydrochloride. Giving the relative large volume of local anesthetics required for adequate TAP block analgesia, systemic toxicities are a potential complication. However, staying within the reported maximum local anesthetic volumes significantly decreases the risk.

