## 5. Methods and Study Design

This is a randomized controlled trial designed to test efficacy of 4Q-TAP against TEA (routine of care) on quality of recovery 48 hours after CRS-HIPEC surgery. All patients will be enrolled at MD Anderson Cancer Center.

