#### ***D. Data collection and measurements***

**Preoperative data:** Demographic data to be obtained includes height (cm), weight (kg), age (yr), gender, (ASA) physical status, and self-declared ethnicity. Patients will be questioned for social history (tobacco) and medical history to calculate Charlson comorbidity index score. QoR 15 will be obtained before surgery. Pain meds (type, dose and frequency)

The following **intraoperative data** will be obtained from electronic medical records: surgery and anesthesia time, surgery type and extent of resection, intraoperative chemotherapy (type and dose), highest temperature, intraoperative anesthetic and opioid consumption. Blood loss, fluid therapy and urinary output will also be collected at the end of surgical procedure.

The following **postoperative data** will be obtained from electronic medical records: Postoperative opioid consumption, breakthrough pain medication requirements and oxygen requirements in PACU and in nursing floor (first 48 hours postoperatively). QoR score and pain scores will be obtained on postoperative day 1, 2, 3, 5, 7, 10( $\pm$ 1) and 30( $\pm$ 2) days if the patient is still admitted to the hospital. Nausea and vomiting, requirement of antiemetics, pruritus, requirement of antihistaminic medications and requirement of naloxone in PACU and first and second postoperative morning after surgery will be collected. Ambulation time, flatus and bowel movements (first time), constipation, length of stay will be obtained. Incentive spirometry will be measured on postoperative day 1 and 2. Postoperative complications (Clavien-Dindo scale during hospital admission) and perioperative morbidity scores (POMS day 7) will be obtained from medical records and 30 days after surgery. Preoperative and postoperative routine laboratory data results will also be collected from electronic medical records.

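### The primary endpoint is QoR-15 at 48 hours, but the statistical section builds the tested change score on a QoR-15 given at about 26 hours

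*Combined protocol and SAP*

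**What the plan says.** Four places in the combined protocol and SAP put the primary question at 48 hours.

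- Section 1, Study Synopsis, Primary Endpoint Definition: "Quality of recovery (QoR) 48 hours after CRS-HIPEC surgery".
- Section 1, Study Synopsis, and Section 3, Study Aims: the primary aim compares the two techniques "on the quality of recovery 48 hours after CRS-HIPEC surgery".
- Section 3, Study Aims: the hypothesis under the primary aim is non-inferiority at 48 hours.
- Section 5, Methods and Study Design: the trial tests efficacy "on quality of recovery 48 hours after CRS-HIPEC surgery".

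The Statistical Considerations section begins with how the primary objective will be evaluated. It describes the preoperative questionnaire and then says "patients will be provided postoperative QoR-15 approximately 26 hours after surgery". It goes on to compute within-patient changes from baseline and compare them between arms, and applies the margin of 10 units to the postoperative change.

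The secondary QoR endpoints in the Synopsis are "QoR on postoperative day 3, 7 10 and 30". The data collection section says "QoR score and pain scores will be obtained on postoperative day 1, 2, 3, 5, 7", followed by days 10 and 30.

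**The concern.** The time of assessment is part of the definition of the primary variable. Here the section that specifies the test gives a different time from the section that defines the endpoint, and the document has no rule of precedence. QoR is collected on both postoperative day 1 and postoperative day 2, so both scores will exist, and an analyst could use either and cite the plan in support.

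The two times ask different questions. The background section gives duration as the reason for the liposomal formulation: "The longer duration of analgesia (48-72 hours) with the use of liposomal bupivacaine presents advantages over traditional local anesthetics". A score at about 26 hours falls before that window and cannot show whether recovery in the block arm is still non-inferior at 48 hours. The trial also has an interim look with stopping rules for both efficacy and futility, so the choice of score could decide whether it stops early. That choice has to be fixed in advance.

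**Working it through.** **1. The time points side by side**

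| Place | Time of QoR |
|---|---|
| Synopsis, Primary Endpoint Definition | 48 h |
| Synopsis and Study Aims, primary aim | 48 h |
| Study Aims, primary hypothesis | 48 h |
| Methods and Study Design | 48 h |
| Synopsis and Study Aims, secondary QoR | days 3, 7, 10, 30 |
| Data collection and measurements | days 1, 2, 3, 5, 7, 10, 30 |
| Statistical Considerations, postoperative score behind the tested change | about 26 h |

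The gap is 48 − 26 = 22 hours. A 26-hour score is close to the day 1 collection but is neither the primary nor a listed secondary endpoint.

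**2. Does any other text settle it?** The outcome definition for quality of recovery names the QoR-15 but gives no time. The paragraphs on margin, sample size and interim analysis give none. The t-test and regression on change scores, described under the Safety heading, give none. The heading Primary Outcome Analysis has no text beneath it. Figure 1 could not be seen here; whatever it shows, the written conflict would remain.

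**3. Does the sample size depend on the time point?** Inputs from Statistical Considerations: margin 10, SD 23, one-sided alpha 0.05, power 80%, one interim after 70 patients with efficacy at p < 0.006 and futility at p > 0.367, about 140 patients. Allocation is 1:1 (Interventions).

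- Source of the SD: the cited before-and-after change is −22 (95% CI −26 to −18) in 127 adults. The half-width is 4, so SD = 4/1.96 × √127 = 23.0. It comes from that study's single change score, and the plan does not say that it holds at 48 hours.
- Fixed design: n per arm = 2 × (1.645 + 0.842)² × 23² / 10² = 65.4, so 66 per arm and 132 in total.
- With the interim at half the information and overall one-sided alpha held at 0.05, power at 140 patients is 80.1% if futility is non-binding and 80.9% if binding. The plan's 140 is therefore reproduced.

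None of these steps uses an assessment time. Replacing 26 hours with 48 hours leaves 140 as it is, unless the SD of the 48-hour change differs from 23.

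**4. Illustration if the 48-hour SD is not 23.** The documents give no 48-hour SD, so 20, 26 and 29 are assumptions. Method: normal approximation, true difference 0, 35 per arm at the interim with the stated boundaries, and p < 0.05 at the end (the final boundary is not stated, so this is also an assumption). At SD 23 and 70 per arm, the expected z-values are 10/(23 × √(2/35)) = 1.82 at the interim and 10/(23 × √(2/70)) = 2.57 at the end. Power is 24.4% (efficacy stop at the interim) + 56.1% (continue, then succeed) = 80.5%.

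| SD at 48 h | Power, 70 per arm | Power, 80 per arm |
|---|---|---|
| 20 | 89% | 91% |
| 23 | 80.5% | 84% |
| 26 | 72% | 75% |
| 29 | 63% | 67% |

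The 80-per-arm column uses the 160 randomized patients in the Synopsis; the 70-per-arm column uses the 140 in Statistical Considerations.

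**The case against.** The strongest reply is that 26 hours is a stray figure. The sentence also carries a questionnaire completion time and cites the external study that supplied the SD, so the number may describe that study. One sentence would then stand against an explicit endpoint definition, an aim, a hypothesis and a design statement that all say 48 hours, and a sensible analyst would follow those. This is plausible, and it is why the point is put as a conflict and not as proof that the aim goes untested. It does not remove the conflict: the sentence says what this trial's randomized patients will be given and points to this trial's schema.

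Three further objections stand in part.

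- The power range does not measure the defect. Uncertainty about the SD would exist even if the section said 48 hours. The table is an illustration; the defect's own size is the 22-hour gap.
- The empty heading is weak evidence by itself. Analysis text for the QoR-15 change appears under Safety, and the headings may be misplaced. That text names no time either, so it does not help.
- The background statement on duration compares liposomal bupivacaine with traditional local anesthetics, not with an epidural. It supports the importance of the later time only indirectly.

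**Conclusion.** The concern holds. The endpoint, aim, hypothesis and design statement say 48 hours. The section that specifies the test says about 26 hours, and no other text says which score is used. Taken literally, that section would run both the interim look (70 patients) and the final analysis 22 hours before the stated endpoint. It must be corrected, because it leaves the primary variable ambiguous in a non-inferiority trial with early stopping.

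The correction does not by itself change the sample size. The conclusion does not rest on the power figures, which depend on assumed SDs and an assumed final boundary. It does rest on reading the text without Figure 1.

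**What to change.** 1. In Statistical Considerations, replace the 26-hour time with the 48-hour (postoperative day 2) QoR-15 and give a window in hours from the end of surgery. The window goes beyond the contradiction itself, but it is needed because the collection schedule is given in days. If 26 hours describes only the cited study, say so.
2. Under Primary Outcome Analysis, define the primary variable as the change in QoR-15 total score from the preoperative baseline to that 48-hour score, and state that it is used at both the interim and the final analysis.
3. Check that Figure 1 shows the same time.
4. State that the SD of 23, taken from the cited study's before-and-after change, is assumed to hold at 48 hours.

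The cost is wording only. QoR is already scheduled on postoperative day 2, read here as the assessment nearest 48 hours, so no visit or data item is added.

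### The printed non-inferiority null has the wrong sign: tested literally, a 4Q-TAP arm exactly at the inferiority limit would be declared non-inferior in 99.97% of trials instead of 5%

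*Combined protocol and SAP*

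**What the plan says.** All of the following is in the Statistical Considerations section of the combined protocol and SAP.

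- **Direction of the scale.** The QoR-15 total runs from 0 to 150, "where higher total scores indicate better quality of recovery".
- **Analysed quantity.** "Within patient changes from baseline will be computed for each treatment arm", and these changes are compared between arms.
- **Sign convention.** Declines are written as negative numbers. The cited study is summarised as "the reported mean change in QoR-15 before and after surgery is -22 (95%CI: -26 to -18) based on 127 adults", and TEA is assumed to change by -25.
- **Margin.** The margin is 10 units. The text assumes that "the average change in QoR-15 for the 4Q-TAP Block treatment arm would be no greater than -35". The footnote to the sample-size table says "A non-inferiority margin of 10 implies the Avg. Change for TAP will be -35" and obtains 10 as -25 minus -35.
- **Hypotheses.** The null is "H_0: \mu_{4Q-TAP\ Block} - \mu_{TEA} \geq 10.0". The alternative is that the same difference equals 0. A note adds that rejecting the null "implies non-inferiority".
- **Use of the test.** It is a one-sided t-test at 0.05. An interim analysis after 70 randomised patients stops for efficacy if p < 0.006 and for futility if p > 0.367.

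**The concern.** On post-minus-pre scores where higher is better, inferiority of 4Q-TAP is a negative value of 4Q-TAP minus TEA. The printed null sits on the positive side. It describes a 4Q-TAP arm at least 10 points better than TEA, and rejecting it is compatible with 4Q-TAP being any amount worse.

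The table footnote reaches +10 only by subtracting in the opposite order (TEA minus 4Q-TAP), so the plan gives two incompatible directions for one margin. The alternative, a single point at 0, is not the complement of the null and does not settle the direction. The phrase that 4Q-TAP would be no greater than -35, read literally on negative scores, puts 4Q-TAP at or below the limit, where it is unacceptable.

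This is the only test stated for the primary hypothesis, and the interim p-values have no other defined test. Programmed as printed, it would pass an inferior technique, stop early for efficacy when 4Q-TAP is doing worse, and tend to stop for futility when 4Q-TAP is doing better.

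**Working it through.** **Inputs (Statistical Considerations unless noted).** SD of change 23 in each arm; margin 10; one-sided alpha 0.05; TEA -25; 4Q-TAP at the limit -35; 140 patients, 70 per arm under the 1:1 allocation (Interventions); interim at 70 patients, 35 per arm. The Synopsis gives 160 randomised, 80 per arm. Let D = 4Q-TAP minus TEA, with change = post minus pre.

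**Step 1: the plan's own figures.**

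- SD from the cited confidence interval: sqrt(127) x 8 / (2 x 1.96) = 23.0, as the plan states.
- A fixed design with D = 0 needs 66 per arm (132 in total) by the normal formula, or 67 per arm (134) by the t-test.
- Adding the interim look with the stated boundaries, and solving for the final critical value at overall one-sided 0.05, gives power at 140 patients of 80.1% (non-binding futility) or 80.9% (binding). The stated 140 reproduces as a group-sequential size.

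**Step 2: where the limit lies.** D at the limit = -35 - (-25) = -10. The printed null is D >= +10, so the limit falls where the printed null is false.

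**Step 3: the final test, 70 per arm.** SE = 23 x sqrt(2/70) = 3.89; t(0.95, 138 df) = 1.656.

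- Printed rule: reject if (Dhat - 10)/SE < -1.656, that is, if Dhat < 10 - 1.656 x 3.888 = +3.56.
- Corrected rule: reject if (Dhat + 10)/SE > 1.656, that is, if Dhat > -3.56.

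Probability of declaring non-inferiority (noncentral t):

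| True D | Printed test | Corrected test |
|---|---|---|
| -20 | >99.99% | 0.001% |
| -10 | 99.97% | 5.0% |
| -5 | 98.6% | 35.8% |
| 0 | 82.0% | 82.0% |
| +5 | 35.8% | 98.6% |
| +10 | 5.0% | 99.97% |

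With 80 per arm, the printed test gives 99.99% at D = -10. With the interim boundaries at 140 patients it gives 99.9%, and the corrected test 4.7% to 5.0%.

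**Step 4: the interim, 35 per arm.** SE = 23 x sqrt(2/35) = 5.50, 68 df. The critical t is 2.581 for p < 0.006 and 0.341 for p > 0.367.

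- Printed efficacy rule: stop if Dhat < 10 - 2.581 x 5.498 = -4.19, that is, only when 4Q-TAP is observed to be more than 4 points worse. At a true D of -10 this happens in 85.1% of trials (corrected test: 0.6%).
- Printed futility rule: stop if Dhat > 10 - 0.341 x 5.498 = +8.12, that is, when 4Q-TAP is observed to be more than 8 points better. At a true D of +10 this happens in 63.3% of trials (corrected test: 0.05%).

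**Step 5: why the sample size does not reveal it.** The two tests mirror each other about D = 0, and the design is powered exactly there, so both give 82.0% at 70 per arm.

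**The case against.** The strongest reply is that the intent is plain. The aims, the rationale and the prose before the hypotheses all speak of non-inferiority, and the -25 and -35 figures show which way the margin should run. The error rates above describe the literal formula and arise only if it is programmed as printed. That condition is accepted. But the section says this hypothesis test will be used to evaluate the trial, and nothing later overrides it: no text appears under Primary Outcome Analysis, and the t-test described under Safety has no margin or direction.

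A second reply is that the means might denote the size of the decline (pre minus post). The null would then be correct, 35 - 25 = 10, and no greater than -35 could be read as a drop of no more than 35. This may well explain how the slip arose, and that phrase is fairly called ambiguous. The plan never defines the means this way, however, and prints every change as a negative number.

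Third, Figure 2, titled as the non-inferiority assessment, is not available in the text reviewed and may show the intended direction. It could not make the printed null agree with negative change scores.

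Finally, writing the alternative as 0 can be seen as naming the point at which the trial is powered. That is loose notation and adds no separate error rate.

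**Conclusion.** The concern holds: the null hypothesis is wrong as written and contradicts the plan's own change scores and table footnote. Applied literally, the final test has an error rate of 99.97% at the inferiority limit instead of 5% (99.9% with the interim boundaries included), and both interim stopping rules work in reverse.

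The figures assume normally distributed changes, SD 23 in both arms, and all patients analysable (70 per arm at the end, 35 per arm at the interim). Because the plan analyses per protocol, actual numbers may be smaller; that would move the percentages somewhat but not the direction of the error. Correction is needed before any interim or final analysis is run.

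**What to change.** 1. Define change explicitly as post-operative minus pre-operative QoR-15 total.
2. Replace the hypotheses with H0: mu(4Q-TAP) - mu(TEA) <= -10 against Ha: mu(4Q-TAP) - mu(TEA) > -10.
3. State the decision rule: non-inferiority is concluded if the lower one-sided 95% confidence bound for 4Q-TAP minus TEA is above -10, with the bound's level adapted to the group-sequential final critical value.
4. Compute the interim p-values for both boundaries from this same test.
5. Reword the margin sentence so that the 4Q-TAP mean change is to be no lower than -35, and write the footnote's subtraction in the same order as the hypotheses: -35 - (-25) = -10.
6. Check that Figure 2 shows the same direction.

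The cost is wording in the statistical section, plus the plan's ordinary amendment procedure. The margin, SD, sample size and stopping boundaries do not change.
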